4.1 Primary objective

The primary objective of this trial is to evaluate whether PFS time, as assessed by an IRC, in subjects receiving cetuximab in combination with cisplatin plus 5-FU is longer than that in subjects receiving cisplatin plus 5-FU alone in the first-line treatment of recurrent and/or metastatic SCCHN.

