5.6 Definition of End of Trial

The trial will be terminated when the last subject has discontinued the trial treatment or OS cut-off, whichever is later.

The OS cut-off will occur when the following conditions are met:

- Follow-up after the randomization of the last subject is at least 12 months, OR
- At least 180 deaths have been reported in this trial.

Investigational Medicinal Product and Other Drugs Used in the Trial

In this trial, trial treatment consists of cetuximab and cisplatin plus 5-FU. Cetuximab is considered as the IMP and cisplatin plus 5-FU as the background first-line standard chemotherapy for recurrent and/or metastatic SCCHN. If cisplatin results in a nonhematologic toxicity (see Section 6.4.1.2.2), cisplatin may be replaced by carboplatin in subsequent cycles.

Cisplatin, carboplatin, and 5-FU are commercially available cytotoxic agents for the treatment of various cancers, including SCCHN. The chemotherapeutic drugs for this trial will be supplied by the local pharmacy/the third party vendor at each trial center. The Sponsor will provide financial compensation for the cost of chemotherapeutic drugs depending on the procedures of each participating center.

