6.4.1.1.2 Carboplatin

If cisplatin results in a nonhematologic toxicity (see Section 6.4.1.2.2), carboplatin at a dose of target AUC=5 may be used as the replacement of cisplatin in subsequent cycles. The decision needs to be made in discussion with the Medical Monitor on a case-by-case basis.

Carboplatin will be administered using an intravenous infusion of 15 minutes or longer (refer to China package insert) on Day 1 of each 21-day treatment cycle. The dose of carboplatin will be calculated considering the subject's renal function as described by the glomerular filtration rate using the Calvert formula or the Chatelut formula, given that the target AUC is 5.

For those subjects in Arm A, there must be at least 1 hour between the end of the cetuximab infusion and the start of the carboplatin infusion.

Exact documentation of the actual doses, dates, and start and end times of infusions is mandatory.

6.4.1.1.3 5-Fluorouracil

Investigators should treat subjects with commercially available forms of 5-FU, and must refer to the approved 5-FU prescribing information on dosage and administration, safety issues (warnings, precautions), adverse reactions, dose reductions and omissions. Investigators should also follow their related local practice for the administration of 5-FU.

5-Fluorouracil will be administered as a dose of 750 mg/m²/day as a continuous intravenous infusion over 24 hours a day from Day 1 to Day 5 (± 6 hours of the overall duration) of each 21-day treatment cycle. Administration of 5-FU is to start upon completion of cisplatin/carboplatin administration and may be performed via the same infusion line.

For those subjects in Arm A, there must be at least 1 hour between the end of the cetuximab infusion and the start of the 5-FU infusion.

Exact documentation of the actual doses, dates, and start and end times of infusions is mandatory.

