6.4.1.2 Dose Reductions of Chemotherapy

Every effort will be made to administer the full doses of cisplatin/carboplatin and 5-FU.

Dose reductions are always based on the dose of the previous cycle. Only 2 dose reductions for cisplatin and 5-FU and 1 dose reduction for carboplatin are permitted. If further toxicity occurs or the criteria for resuming treatment are not met, the subject must be withdrawn from chemotherapy (see Table 6.5).

Table 6.5 Dose Reductions for Chemotherapy

	Dose reduction levels	Dosage ¹
Cisplatin	0	75mg/m ²
	-1 (decreased by 20%)	60mg/m ²
	-2 (decreased by 20% from -1 level)	48mg/m ²
Carboplatin ² -	0	AUC 5
	-1 (decreased by 20%)	AUC 4
5-Fluorouracil	0	750mg/m ²
	-1 (decreased by 20%)	600mg/m ²
	-2 (decreased by 20% from -1 level)	480mg/m ²

Abbreviation: AUC, area under serum concentration time curve.

- 1 The doses which have been reduced for toxicity must not be re-escalated.
- 2 Carboplatin can be considered, if the subject experiences a nonhematologic toxicity. The starting dose of carboplatin would be the first dose level of AUC 5 at the Investigator's discretion.

Dose adjustments are to be made according to the body system showing the greatest degree of toxicity experienced during the previous cycle. Toxicities will be graded using the CTCAE version 4.03.

All implemented dose reductions are permanent. The doses must be modified according to the lowest hematology values and the highest degree of nonhematologic toxicities observed at the scheduled date of chemotherapy. If a subject develops several different toxic effects and there are conflicting recommendations, the dose modification will be based on the AE on the scheduled day of treatment.

Dose reduction and delays and related management will be documented in the subject's medical record and in the related section in the eCRF.

If a subject has a Grade 3 or 4 toxicity after 2 dose reductions, or if a treatment delay is longer than 3 consecutive weeks, then the discontinuation of chemotherapy treatment has to be considered.

For those in Arm A, chemotherapy will not be delayed for cetuximab-related toxicities.

Major toxicities observed with cisplatin: nephrotoxicity; ototoxicity; myelodepression with leukopenia, thrombocytopenia and anemia; infectious complications; nausea and vomiting; and peripheral neuropathies.

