6.4.1.2.2 Nonhematologic Toxicities

If a subject has a Grade 3 or 4 toxicity, as defined in Table 6.8, after 2 dose reductions, or if a treatment delay is longer than 3 consecutive weeks, then the discontinuation of chemotherapy treatment has to be considered.

Table 6.8 Criteria for Dose Reductions Based on Nonhematologic Toxicities on the Scheduled Day of Treatment

Toxicity	Grade ¹	Action to be taken
Mucositis	Grade 1	Delay chemotherapy treatment until Grade 0
	> Grade 1	Delay chemotherapy treatment until Grade 0; dose reduction of all further doses of 5-FU only by 20%
Diarrhea	Grade 1	Delay chemotherapy treatment until Grade 0
	> Grade 1	Delay chemotherapy treatment until Grade 0; dose reduction of all further doses of 5-FU only by 20%
Hypercreatinemia	≥ Grade 1	Delay chemotherapy treatment until Grade 0, change cisplatin to carboplatin
Ototoxicity	Grade 2	Dose reduction of all further doses of cisplatin by 20%
	> Grade 2	Delay chemotherapy treatment until ≤ Grade 2, change cisplatin to carboplatin
	> Grade 3	Stop carboplatin
Hand-foot syndrome	Grade 2	Delay chemotherapy treatment until ≤ Grade 1
	> Grade 2	Delay chemotherapy treatment until ≤ Grade 1; dose reduction of all further doses of 5-FU by 20%
Other organ toxicity ²	Grade 2	Delay chemotherapy treatment until Grade 1
	> Grade 2	Delay chemotherapy treatment until Grade 1 ³ ; dose reduction of all further doses of platinum-based treatment and 5-FU by 20% (or dose reduction of carboplatin to AUC 4 if applicable)
Sensory neuropathy	Grade 2	Dose reduction for all further doses of cisplatin by 20%
	> Grade 2	Stop cisplatin, change cisplatin to carboplatin
	> Grade 3	Stop carboplatin

5-FU: 5-fluorouracil.

The results of hematology and blood biochemistry analyses must be available before the start of each cycle of chemotherapy.

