6.4.2 Other Drugs

Subjects must be given an antihistamine and a corticosteroid at least 1 hour before receiving the first infusion of cetuximab (see Section 6.2.1). All pretreatment must be documented in the eCRF.

¹ Graded according to Common Terminology Criteria for Adverse Events, version 4.03.

² Except asymptomatic increase in transaminases, cetuximab-induced skin reactions and medically irrelevant side effects (e.g., nausea, alopecia, altered taste).

Nonhematologic chemotherapy-related toxicities have resolved to ≤ Grade 1 or baseline (excluding weight loss, skin reactions, paronychia, fatigue, ototoxicity or neurotoxicity which must have resolved to ≤ Grade 2).

The prophylactic drugs will be prescribed via the hospital pharmacy at each trial center. The Investigator should administer the drugs in accordance with the information given in the product package insert with respect to dosage and administration, safety issues (warnings, precautions), adverse reactions, dose modifications and omissions. The Investigator should also follow any related local practices for the administration of such pretreatment. The Sponsor will not assume the costs for these pretreatment drugs.

Subjects must receive hydration treatment, medication to maintain urinary output and antiemetic prophylaxis for each cisplatin infusion as outlined in Section 6.4.1.1.1. Centers should follow their related local practices and the approved local package insert or the scheme outlined in Section 6.4.1.1.1. All of these drugs and infusions must be documented in the eCRF.

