**Definition of pre-treatment value:**

The last non-missing measurement prior to the first trial drug administration will be used as the pre-treatment baseline measurement. Definition of pre-treatment value will be used as baseline for all safety analysis.

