|----------------------------------|--|--------------------------------------|---|---|---|---|---------|--|
|                                  |  |                                      | Grade 1   | Grade 2   | Grade 3   | Grade 4   | Grade 5 |  |
| Monocytes (10E9/L)               | No   |                                      |   |   |   |   |         |  |
| Eosinophils (10E9/L)             | No   |                                      |   |   |   |   |         |  |
| Basophils (10E9/L)               | No   |                                      |   |   |   |   |         |  |
| Platelet (10E9/L)                | Yes  | Platelet count decreased             | <LLN
75,000/mm  ;
<LLN - 75.0 x
10e9/L | <75,000
50,000/mm  ;
<75.0 - 50.0 x
10e9/L | <50,000
25,000/mm  ;
<50.0 - 25.0 x
10e9/L | -
-
<25,000/mm  ;
<25.0 x 10e9/L |         |  |
| Biochemistry              |  |                                      |   |   |   |   |         |  |
| Creatinine (umol/L)              | Yes  | Creatinine increased                 | >1 - 1.5 x
baseline; >ULN -
1.5 x ULN                 | >1.5 - 3.0 x
baseline; >1.5 -
3.0 x ULN                   | >3.0 baseline;
>3.0 - 6.0 x ULN                              | >6.0 x ULN  |         |  |
| Alanine Aminotransferase (U/L)   | Yes  | Alanine aminotransferase increased   | >ULN - 3.0 x ULN  | >3.0 - 5.0 x ULN  | >5.0 - 20.0 x ULN   | >20.0 x ULN   |         |  |
| Aspartate Aminotransferase (U/L) | Yes  | Aspartate aminotransferase increased | >ULN - 3.0 x ULN  | >3.0 - 5.0 x ULN  | >5.0 - 20.0 x ULN   | >20.0 x ULN   |         |  |
| Gamma Glutamyl Transferase (U/L) | Yes  | GGT increased                        | >ULN - 2.5 x ULN  | >2.5 - 5.0 x ULN  | >5.0 - 20.0 x ULN   | >20.0 x ULN   |         |  |
| Total Bilirubin (umol/L)         | Yes  | Blood bilirubin increased            | >ULN - 1.5 x ULN  | >1.5 - 3.0 x ULN  | >3.0 - 10.0 x ULN   | >10.0 x ULN   |         |  |
| Direct Bilirubin (umol/L)        | Yes  | Blood bilirubin increased            | >ULN - 1.5 x ULN  | >1.5 - 3.0 x ULN  | >3.0 - 10.0 x ULN   | >10.0 x ULN   |         |  |
| Lipase (IU/L)                    | Yes  | Lipase increased                     | >ULN - 1.5 x ULN  | >1.5 - 2.0 x ULN  | >2.0 - 5.0 x ULN  | >5.0 x ULN  |         |  |

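### Table 6.8 makes the switch to carboplatin a required action (for creatinine, from Grade 1), other sections make it optional, and the creatinine trigger and recovery grade are not settled

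*Protocol*

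**What the plan says.** **Required.** Protocol 6.4.1.2.2, Table 6.8, lists actions by toxicity on the scheduled treatment day. For creatinine of Grade 1 or more the action is "Delay chemotherapy treatment until Grade 0, change cisplatin to carboplatin". The ototoxicity and sensory neuropathy rows also direct a change to carboplatin, but only above Grade 2. None of these rows has permissive wording or a Medical Monitor step.

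**Optional.** The opening text of Protocol Section 6 says that, after a nonhematologic toxicity, "cisplatin may be replaced by carboplatin in subsequent cycles". Section 5.2, the synopsis and the Table 6.4 footnote say the same in substance, and the Table 6.5 footnote says that carboplatin can be considered. Section 6.4.1.1.2 adds "The decision needs to be made in discussion with the Medical Monitor on a case-by-case basis", as does the synopsis.

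**Recovery.** Section 6.4.1.1.4 allows the next cycle once nonhematologic toxicity is back to Grade 1 or less, or to baseline. The creatinine row of Table 6.8 requires Grade 0.

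**Grading.** Section 6.4.1.2 says "Toxicities will be graded using the CTCAE version 4.03", and the Table 6.8 footnote reads "Graded according to Common Terminology Criteria for Adverse Events, version 4.03". The protocol does not print the creatinine grades. SAP Appendix 3 does, with Grade 1 as ">1 - 1.5 x baseline; >ULN - 1.5 x ULN".

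**Objective.** Section 4.1 asks whether PFS in subjects receiving "cetuximab in combination with cisplatin plus 5-FU is longer than that in subjects receiving cisplatin plus 5-FU alone".

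**The concern.** Several of the optional statements cite Section 6.4.1.2.2, the section that holds Table 6.8. A reader who follows the cross-reference goes from a permission to a directive, and nothing says which governs. For creatinine there are two further gaps. A Grade 1 value permits the next cycle under 6.4.1.1.4 but triggers a delay and a switch under Table 6.8. And if the baseline limb of the CTCAE definition counts on its own, a value just above the subject's own baseline, within the normal range, is already Grade 1.

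At stake is whether sites give the same platinum treatment to the same kind of subject, and how well cisplatin exposure and platinum toxicity can be interpreted afterwards.

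**Working it through.** **1. The passages side by side**

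| Question | Table 6.8, creatinine row | Elsewhere in the protocol |
|---|---|---|
| Is the switch required? | Yes, from Grade 1 | Optional (synopsis, 5.2, 6, 6.4.1.1.2, footnotes to Tables 6.4 and 6.5) |
| Who decides? | Not stated | Case by case with the Medical Monitor (synopsis, 6.4.1.1.2) |
| Recovery before the next cycle | Grade 0 | Grade 1 or less, or baseline (6.4.1.1.4) |
| Which CTCAE limb? | Not stated | Not stated |

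**2. How much the choice of limb matters**

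The documents give no switch rate, so there is no figure to reproduce. What follows is conditional.

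*Inputs from the documents.* At most 6 cycles, so up to 5 later pre-cycle checks (cycles 2 to 6). Baseline for safety analyses is a single value: "The last non-missing measurement prior to the first trial drug administration will be used as the pre-treatment baseline measurement" (SAP Section 11). Planned size is 240, allocated 2:1, so 160 and 80.

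*Baseline limb, no true change.* If the baseline and k later values are exchangeable and there are no ties, the baseline is the largest of the k + 1 values with probability 1/(k + 1). Hence P(at least one value above baseline) = k/(k + 1):
- k = 1: 1/2 = 50%
- k = 2: 2/3 = 67%
- k = 3: 3/4 = 75%
- k = 5: 5/6 = 83%, or 200 of 240 (about 133 of 160 in Arm A and 67 of 80 in Arm B)

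*Rounding and drift.* Simulation of 200,000 subjects, all inputs assumed: centre 70 umol/L, values rounded to 1 umol/L, within-subject CV 3%, 5% and 10%.

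| Mean change | After 1 check | After 5 checks |
|---|---|---|
| None | 44 to 48% | 78 to 82% |
| +5% | 62 to 84% | 91 to 98% |
| -5% | 8 to 34% | 26 to 68% |
| -10% | 0.4 to 21% | 2 to 51% |

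*Fewer cycles because of progression.* Treatment stops at PD, so not every subject has five checks. Since k/(k + 1) is the sum of 1/[j(j + 1)] over j = 1 to k, the weighted share is the sum over j = 1 to 5 of S(21j days)/[j(j + 1)]. S is assumed exponential, with the medians quoted for the EXTREME trial in Protocol 3.7.2 and 1 month = 30.4375 days.
- Median 3.3 months: S = 0.865, 0.748, 0.647, 0.560, 0.485. Sum = 0.4325 + 0.1247 + 0.0540 + 0.0280 + 0.0162 = 0.655, about 66%.
- Median 5.6 months: S = 0.918, 0.843, 0.774, 0.711, 0.652. Sum = 0.4591 + 0.1405 + 0.0645 + 0.0355 + 0.0217 = 0.721, about 72%.

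*ULN limb only.* Five checks, all inputs assumed: between-subject log-SD 0.20, within-subject CV 5 to 10%, ULN 100 to 110 umol/L, mean change 0 to +20%. The share is about 3 to 39%.

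**3. What a switch does to the SAP tables**

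SAP 15.2 divides cumulative cisplatin dose by the duration of cisplatin itself. For a subject switched after one full-dose cycle, duration is (0 + 21)/7 = 3 weeks, dose intensity is 75/(3/3) = 75 mg/m² per 3 weeks, and relative dose intensity is 75/75 = 100%. That figure does not show that cisplatin stopped after one cycle. SAP 17.1 counts an AE with cisplatin withdrawn as leading to chemotherapy discontinuation. A switch coded that way would be counted although platinum treatment continues. SAP Appendix 1 lists no specific deviation for switching, or not switching, against Table 6.8.

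**The case against.** The best defence is that the passages can be read together. The optional wording would be a general summary that points to the table for detail, and the table does not waive the discussion with the Medical Monitor. The switch text also requires a toxicity resulting from cisplatin, which a trivial rise with no attributed cause need not be. The SAP appendix supports laboratory summaries; the SAP modification history dates its addition to 16 April 2018, after planned recruitment was to end in the fourth quarter of 2017. It was not a dosing instruction to sites.

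Part of this stands. A central discussion of each switch would dampen differences between sites, and the literal baseline reading is not the only sensible one. But the optional text cites the very section that holds the directive, the protocol itself applies CTCAE 4.03 to Table 6.8, and no reading settles Grade 0 against Grade 1 or baseline.

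A reader might go further and infer that most subjects would leave the cisplatin regimen named in the objective. The documents do not support that. It needs the baseline limb to count alone, several cycles per subject, and creatinine that does not fall on average. Nor do they show that few would switch under the optional text.

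The reporting gap is also small. SAP 12.1 already counts switches to carboplatin by arm and main discontinuation reasons per drug, and SAP 15.3 tabulates cisplatin and carboplatin by cycle. Only the specific triggering toxicity is missing.

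**Conclusion.** The contradiction holds on the text alone: required against optional for the switch, Grade 0 against Grade 1 or baseline for creatinine recovery, and no stated limb for the creatinine trigger.

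Its size is conditional. With the baseline limb read literally and creatinine truly flat, 44 to 50% of subjects would trigger after one later check and 78 to 83% after five, or about 66 to 72% after weighting for progression. The five-check share is about 2 to 68% if creatinine falls by 5 to 10% on average, and about 3 to 39% if only the ULN limb counts. The CVs, drift, ULN and exponential PFS are assumptions.

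Two stronger inferences should be resisted. The hazard ratio is not shown to be biased: the rule is the same in both arms, the primary analysis is ITT, and carboplatin is protocol treatment (Figure 5.1, Section 6.2.1, Table 6.4). Cisplatin exposure does not become uninterpretable either: the SAP gives each platinum drug its own exposure summary. What remains is inconsistent platinum treatment across sites, and cisplatin exposure and platinum toxicity that are harder to interpret. This is a minor to moderate point, worth correcting because the correction is cheap.

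**What to change.** 1. Reconcile Table 6.8 with the synopsis, Sections 5.2, 6, 6.4.1.1.2 and 6.4.1.1.4, and the footnotes to Tables 6.4 and 6.5. One statement should govern whether the switch is mandatory or case by case, and which recovery grade applies. Cover the ototoxicity and sensory neuropathy rows as well.
2. State in Table 6.8 which limb of the CTCAE creatinine definition is the trigger.
3. Optionally, add the triggering toxicity to the switch count already planned by arm in SAP 12.1.

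The sponsor's medical team must choose the rule; no choice is proposed here. The cost is a wording amendment to Table 6.8 with a footnote, matching edits to the conflicting passages, a clarification letter to sites and, if item 3 is taken up, one extra line in an existing table.

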6.4.2 Other Drugs

Subjects must be given an antihistamine and a corticosteroid at least 1 hour before receiving the first infusion of cetuximab (see Section 6.2.1). All pretreatment must be documented in the eCRF.

¹ Graded according to Common Terminology Criteria for Adverse Events, version 4.03.

² Except asymptomatic increase in transaminases, cetuximab-induced skin reactions and medically irrelevant side effects (e.g., nausea, alopecia, altered taste).

Nonhematologic chemotherapy-related toxicities have resolved to ≤ Grade 1 or baseline (excluding weight loss, skin reactions, paronychia, fatigue, ototoxicity or neurotoxicity which must have resolved to ≤ Grade 2).

The prophylactic drugs will be prescribed via the hospital pharmacy at each trial center. The Investigator should administer the drugs in accordance with the information given in the product package insert with respect to dosage and administration, safety issues (warnings, precautions), adverse reactions, dose modifications and omissions. The Investigator should also follow any related local practices for the administration of such pretreatment. The Sponsor will not assume the costs for these pretreatment drugs.

Subjects must receive hydration treatment, medication to maintain urinary output and antiemetic prophylaxis for each cisplatin infusion as outlined in Section 6.4.1.1.1. Centers should follow their related local practices and the approved local package insert or the scheme outlined in Section 6.4.1.1.1. All of these drugs and infusions must be documented in the eCRF.

6.5 Concomitant Medications and Therapies

The following must be recorded in the eCRF:

- All medication administered during the trial until the safety follow-up visit or EOEA visit, whichever is later, including the generic name, total daily dosage, and duration of treatment.
- All (neo-) adjuvant chemotherapy administered before inclusion in the trial, with start and stop dates, treatment, dose, and regimen.
- Any previous surgery on the underlying tumor (date, extent of surgical procedure).
- Any previous radiotherapy for the underlying tumor (date, dose).
- All diagnostic or therapeutic procedures performed during the trial period (i.e., from signing of informed consent onwards), including the date, indication, description of the procedures, and any clinical findings.
- Any change in the permitted concomitant medications being taken at the beginning of the clinical trial, with the type of medication, dose, duration, and indication.

6.5.1 Permitted Medicines

All subjects, male and female, must practice medically-accepted contraception throughout the trial if the risk of conception exists.

Sedatives, antiemetics, antibiotics, analgesics, antihistamines, steroids, granulocyte-colony stimulating factor, as well as red blood cells, erythropoietin, platelets or fresh frozen plasma transfusions may be given at the discretion of the Investigator according to local practices to assist in the management of pain, infection, and other complications of the malignancy. In the case of febrile neutropenia or documented infection, intravenous antibiotics may be administered for curative use (see Section 6.4.1.2.1). Prophylactic use of quinolone is also permitted in cases of recurrent febrile neutropenia despite dose reduction of chemotherapy.

For any skin AE of Grade 1–3, topical and/or oral antibiotics are permitted (see Section 6.2.2.1). Subjects with Grade 3 or higher reactions should be referred to a dermatologist for advice and management if needed. If pruritus occurs, an oral antihistamine is advised. In case of dry skin, the use of emollient creams is beneficial. Fissures may occur in dry skin and topical dressings are helpful.

Localized radiation therapy for pain relief is permitted providing it is not directed towards an area in which the subject's only available target lesion is located. Any target or nontarget lesion assessed according to RECIST version 1.1 which will be radiated during the trial must not be further considered for response assessment. If any localized radiation therapy during trial treatment, e.g., due to increasing bone pain, is considered, it should always firstly be checked if the subject has PD according to RECIST version 1.1.

Bisphosphonates might be given for bone metastases. If any dose increase of an already ongoing bisphosphonate treatment or the start of bisphosphonate treatment due to increasing bone pain is considered, it should always firstly be checked if this subject might have PD according to RECIST version 1.1

Any medications (other than those excluded by the protocol, see Section 6.5.2) that are considered necessary for the subject's welfare and will not interfere with the trial medication may be given at the Investigator's discretion.

Rescue medications may be administered to address ineffective treatment, anticipated adverse reactions or anticipated emergency situations.

